5.7.2 Covariates

These analyses may be stratified to identify other important factors which may impact nerve recovery such as ag

5.7.3 Planned Subgroups

5.7.4 Missing Data

Every effort will be made to obtain the required data at each scheduled evaluation from all subjects who have been randomized. In assessing the primary efficacy endpoint, a repeated measures mixed model will be utilized on all observed data.

5.7.5 Demographic and Baseline Characteristics

Demographic and baseline characteristics including age, sex, race, type of traumatic injury sustained, nerves that are injured, pain assessments, concomitant treatments, quality of life assessments will be summarized descriptively.

5.8 Efficacy Analyses

5.8.1 Primary Efficacy Endpoint

The primary efficacy endpoint for both the pilot and comparative studies will be the change of VAS score at 3 months compared to baseline for subjects in both the Axoguard® Nerve Cap study arm and the neurectomy control arm.

5.8.2 Secondary Efficacy Endpoints

The secondary efficacy endpoints for the comparative study are VAS, PROMIS® and FHSQ scores at months 1, 3, 6, 9 and 12 compared to baseline; and quantity and class of pain medication use at months 1, 3, 6, 9, and 12 months compared to baseline for subjects assigned to the Axoguard® Nerve Cap. The secondary efficacy endpoints for the comparative study are VAS, PROMIS® and FHSQ scores at months 1, 3, 6, 9 and 12 compared to baseline; and quantity, quality and class of pain medication use at months 1, 3, 6, 9, and 12 months compared to baseline for subjects in both the Axoguard® Nerve Cap study arm and the historical control neurectomy study arm.

All secondary endpoints will be summarized using descriptive statistics by repair type and by study day/time, if appropriate.

5.9 Safety Analyses

The safety endpoints will compare the nature and incidence of AEs between treatment groups. The safety objective is to show that there is no clinically significant difference of product-related adverse events between Axoguard® Nerve Cap and neurectomy study arms. Specifically, AEs, will be analyzed as a group and any change in the incidence rate of the listed AEs post treatment will be noted. AE nomenclature will be standardized according to the Medical Dictionary for Medical Activities (MedDRA)-preferred term and system organ classification. The occurrence of the treatment-emergent AEs (TEAEs) will be summarized by repair type using MedDRA preferred terms, system organ classifications, and severity. All AEs will be listed for individual subjects and summarized by verbatim and preferred terms. Separate summaries of treatment-emergent SAEs and AEs related to repair type will be generated.

Any event reported on the CRF that occurs on or after the treatment will be defined as treatmentemergent. Additionally, it is assumed that an AE, which was reported to have started on Day 0 without an associated onset time, may have occurred after the treatment. Hence, AEs occurring on Day 0 with no defined onset time will also be considered treatment-emergent.

Subject disposition will be presented for all subjects. The number of subjects who completed the study and discontinued from the study will be provided. The reasons for early discontinuation will also be presented.

5.10 Study Success

Study success is defined as demonstrating the reduction in pain by VAS score with the treatment of Axoguard® Nerve Cap is superior to the reduction in VAS score for neurectomy group

In addition, there should be no clinically significant difference of product related adverse events rates following implantation of Axoguard® Nerve Cap compared to neurectomy.

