3. STUDY DESIGN

3.1 Description of Design

This is a multicenter, prospective, randomized, controlled, subject blinded comparative parallel group study in patients presenting with symptomatic neuroma (verified by diagnostic block or imaging (US or MRI confirmation) with a baseline pain level of \geq 65 mm on a 100 mm Visual Analog Scale (VAS) during screening. Fifteen (15) pilot subjects will receive the Axoguard® Nerve Cap in the pilot phase of the study. In the comparative phase of the study, approximately 86 adult subjects meeting inclusion/exclusion criteria will be centrally randomized in a 1:1 ratio to receive either Axoguard® Nerve Cap or neurectomy. This study design overview is found in Figure 3.1. This study is intended to collect post-operative data as well as physician experience surveys on the clinical use of Axoguard® Nerve Cap to evaluate its safety and performance as compared to subjects receiving neurectomy.

Figure 3.1. Study Design

This study will consist of a total of 8 visits

This study will be conducted in

accordance with the FDA regulations21 CFR Parts 50 and 56 and current cGCP requirements as described in the ISO 14155:2011 standards, applicable IRB regulations.

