5. STATISTICAL CONSIDERATIONS

Descriptive statistical methods will be used to summarize the data from this study. Unless stated otherwise, the term "descriptive statistics" refers to number of events (n), mean, median, standard deviation (SD), standard error, minimum, maximum, and coefficient of variation (CV) for continuous data and frequencies and percentages for categorical data. All data collected during the study will be included in data listings. Unless otherwise noted, the data will be sorted by subject number, and then by date within each subject number.

Unless specified otherwise, all statistical testing will be two-sided and will be performed using an overall significance (alpha) level of 0.05.

All statistical analyses will be conducted with the SAS® System, version 9.1.3 or higher.

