7.1. Sample Size and Power

A total of 101 participants (15 pilot; 86 comparative/randomized) at up to 20 sites will be enrolled.

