8.2. Control of Type 1 Error

Type I error will not be controlled in this study in order to understand the potential benefits of Axoguard Nerve Cap regardless of the studywise error rate.

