9.3.2. Analyses

All AEs will be summarized by seriousness, relatedness to the treatment (as assessed by the participant's physician) and severity. All AEs will be listed for individual participants.

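### Study success includes a no-difference condition on adverse events that has no visible margin or decision rule, and about 43 subjects per arm leave wide uncertainty about that difference

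*Protocol*

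**What the plan says.** Protocol 5.10 defines success as superiority on VAS pain and then adds that "there should be no clinically significant difference of product related adverse events rates" after implantation compared with neurectomy. Protocol 5.9 states the matching aim: "The safety objective is to show that there is no clinically significant difference of product-related adverse events" between the arms. The same section says that AE incidence will be compared between groups and that treatment-emergent events will be tabulated by repair type.

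The SAP's safety analysis (9.3.2) is one of summary and listing: "All AEs will be summarized by seriousness, relatedness to the treatment (as assessed by the participant's physician) and severity". It names no between-arm difference, interval, test or limit. The visible text of the SAP contains no definition of study success.

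The sample size is in SAP 7.1: "A total of 101 participants (15 pilot; 86 comparative/randomized) at up to 20 sites will be enrolled". Protocol 3.1 says that comparative-phase subjects are "centrally randomized in a 1:1 ratio to receive either" the cap or neurectomy. Protocol 5 sets a general default, "Unless specified otherwise, all statistical testing will be two-sided and will be performed using an overall significance (alpha) level of 0.05", but ties it to no AE comparison. SAP 8.2 says that "Type I error will not be controlled in this study".

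The two documents define the safety population differently. Protocol 5.5.2 takes in only subjects who had the device inserted. SAP 7.4.4 takes in both arms.

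**The concern.** Showing that two rates do not differ by a clinically important amount is an equivalence or non-inferiority claim. It needs a stated amount, an interval or test that can rule that amount out, and enough subjects to do so. Here the aim and the success condition are stated, but none of these three is visible. The condition would then be settled after the data are seen, from tables of counts.

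The comparison is of an implant added to neurectomy with neurectomy alone (SAP, introductory description). Protocol 1.3.3 says there are no published clinical data on this device. A declaration of success would carry an implied statement of comparable safety, and the planned tables could look similar while the data remain compatible with a sizeable excess.

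**Working it through.** **Inputs.** 86 randomized (SAP 7.1) at 1:1 (Protocol 3.1) gives 86/2 = 43 per arm. The figure of 86 cannot be reproduced: the visible text gives no VAS difference, SD, power or dropout rate, and no AE rate. All AE rates and margins below are therefore assumptions, shown over a range.

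**Step 1: precision.** With the same rate p in both arms, SE = sqrt(2p(1−p)/43), and the 95% half-width is 1.96 × SE. At p = 0.05, SE = sqrt(0.095/43) = 0.0470 and the half-width is 9.2 points.

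**Step 2: ability to exclude an excess.** If the true rates are equal, the chance that the upper limit of the two-sided 95% interval falls below a margin m is approximately Φ(m/SE − 1.96). At p = 0.05 and m = 0.10 this is Φ(2.13 − 1.96) = 57%. An exact enumeration with the Newcombe limit gives the second figure in each cell. The smallest margin with 80% power is (1.96 + 0.84) × SE.

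| Assumed rate per arm | 95% half-width (points) | Power, 10-point margin (normal / Newcombe) | Power, 15-point margin (normal / Newcombe) | Smallest margin at 80% power, normal (points) |
|---|---|---|---|---|
| 2% | 5.9 | 91% / 64% | 99.9% / 89% | 8.5 |
| 5% | 9.2 | 57% / 45% | 89% / 75% | 13.2 |
| 10% | 12.7 | 34% / 31% | 64% / 58% | 18.1 |
| 20% | 16.9 | 21% / 21% | 41% / 41% | 24.2 |

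For a 5-point margin at a 5% rate, power is 19% (normal) or 12% (Newcombe).

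**Step 3: a hypothetical rule.** Suppose the condition counted as met whenever a two-sided Fisher test at 0.05 was non-significant. The chance of passing, enumerated over two binomials at 43 v 43, is:

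| True rates, control v cap | Passes |
|---|---|
| 5% v 10% | 94.9% |
| 5% v 15% | 78.9% |
| 10% v 20% | 83.1% |
| 20% v 30% | 86.7% |
| 10% v 30% | 44.8% |
| 5% v 25% | 31.9% |

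Fisher is conservative. A pooled z test gives 74.8% in place of 83.1% for 10% v 20%.

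**Step 4: two edge cases.** Zero events in 43 leaves an exact upper limit of 1 − 0.025^(1/43) = 8.2%. With no control events, 6 of 43 (14%) in the cap arm are needed for Fisher p ≤ 0.05.

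**Step 5: pilot data.** Protocol 5.6 includes the 15 pilot subjects in the final analyses, while SAP 8.1 analyses the phases separately. Pooling gives 58 v 43, and 10% v 20% would still pass the Step 3 rule in 77.6% of trials.

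**The case against.** Several points on the other side have force.

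- **No passage judges safety by a non-significant test.** The wording is about clinical significance, which is a judgement of size, and SAP 9.3.2 names no AE test. A reader might infer that absence of significance is the criterion. The documents do not support that, so Step 3 only illustrates one rule that could fill the gap.
- **A reader might infer that 43 per arm can never show comparable safety.** That is too strong. It depends on the rate and the margin, and neither is visible. With rates of 2% to 5% and a 15-point margin, power is 75% to 99.9%, depending on rate and method.
- **A reader might infer that the condition is met almost by default.** Even under the hypothetical rule this fails for large excesses: 10% v 30% passes in 45% of trials and 5% v 25% in 32%.
- **A margin may exist in text we cannot see.** The contents list a section on hypotheses (5.3) that does not appear, and 5.4 shows only counts. The finding is that none is visible. Protocol 5.9, 5.10 and SAP 9.3.2 refer to none.
- **Tables by arm are already planned.** Protocol 5.9 covers these, and Protocol 3.5.1 and SAP 9.3.1 set the time points. What is new in the fix is the difference and its interval.
- **The condition concerns product-related events, and the control arm receives no product.** If only device-related events count, the control rate is zero by construction and two-rate comparisons such as 10% v 20% do not apply. The calculations here are for AE rates that can occur in both arms. How relatedness is defined for the control arm is a separate question.

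These points limit the size of the claim. They do not supply the missing decision rule.

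**Conclusion.** The concern holds in limited form. The protocol aims to show a lack of clinically important difference in AEs and makes it part of success, while no visible passage says what would establish it and the SAP plans description only. At 43 per arm and AE rates of 5% or more, the chance of excluding a 10-point excess is 45% to 57% at a 5% rate, about one in three at 10% and about one in five at 20%. Smaller excesses are harder still to exclude.

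This rests on the derived 43 per arm with no dropout, equal true rates, and assumed event rates. The descriptive tables alone cannot support a statement of comparable safety. The documents do not establish that the trial could not meet any reasonable margin, or that the condition would pass whatever the truth.

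**What to change.** - **Protocol 5.9 and 5.10:** replace the aim of showing no clinically significant difference with estimating the difference. Say that failing to observe a difference will not be presented as demonstrated comparable safety.
- **SAP 9.3.2:** at 3, 6, 9 and 12 months, report by arm the proportion of subjects with at least one AE and with at least one SAE, and the between-arm difference with a two-sided 95% confidence interval. Use the SAP 7.4.4 safety population. State that the trial is not sized to exclude a difference.
- **Protocol 5.5.2:** align it with SAP 7.4.4. As worded it leaves the two-arm table without a control group.
- **If safety stays in the success definition:** name the AE endpoint and time point, a justified margin and the confidence-interval rule, and state the power at 43 per arm. Whether to keep it there is the sponsor's choice. Removing it leaves success resting on VAS pain alone.

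The cost is wording in three protocol sections and one SAP table, with no new data collection. The sponsor gives up a no-difference safety claim that the present plan does not support.

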4.4 Relationship to Study Product or Control Procedure

The Investigator will assess the relationship of each adverse event to the study product and study procedure, using the criteria outlined in Table 4.4-1.

Table 4.4–1: Relationship of Adverse Events to Study Product or Control Procedure

Relationship	Description
Unrelated	An AE that is clearly and uncontrovertibly due to extraneous causes (disease,
	environment, etc) and does not meet the criteria for study device relationship listed
	under possible or probable.
Possible	An AE may be considered as possibly related if:
	1) it cannot be reasonably explained by the subject's clinical state or by
	environmental or toxic factors; or
	it follows a reasonable temporal sequence from administration of study device;
	or,
	3) it follows a known pattern of response to the study device.
Probable	An AE considered, with a high degree of certainty, to be related to the study
	device. An AE may be considered probably related to study device if:
	1) it cannot be reasonably explained by the known characteristics of the subject's
	clinical state or by environmental or toxic factors;
	and at least one of the following is true:
	2) it follows a reasonable temporal sequence from administration of study device;
	it follows a known pattern of response to study device;
	4) it disappears or decreases upon removal
Definitely	An AE that is clearly and uncontrovertibly due to study device.
Related	

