This document describes the statistical methods and data presentations to be used in the analysis of data from the post-market study, "Axogen Protocol CAP-CP-001: A Multicenter, Prospective, Randomized, Subject-Blinded Comparative Study of Axoguard® Nerve Cap and Neurectomy for the Treatment of Symptomatic Neuroma and Prevention of Recurrent End-Neuroma Pain "REPOSE."

Background information is provided for the overall study design and objectives in the study protocol (current version 3.0 dated 01MAR2021). Refer to the study specific data management plan and case report forms (CRFs) for additional details of study conduct and data collection.

The study evaluates symptomatic neuromas in the foot or ankle and will occur in two phases: a pilot study and a comparative study. The pilot phase study is a prospective single arm series in which all participants receive the Axoguard Nerve Cap following neurectomy. The comparative phase study is a prospective, randomized, controlled, participant-blinded comparative cohort comparing participants who receive the Axoguard Nerve Cap following neurectomy (Treatment) to those who undergo neurectomy alone (Control).

3. Objectives

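### The product-related safety criterion does not fit a control arm that receives no product; the Protocol safety set and the adverse-event recording rules also need aligning

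*Protocol*

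**What the plan says.** **Criterion.** Protocol 5.10 makes safety part of study success, requiring "no clinically significant difference of product related adverse events rates following implantation of" the cap relative to neurectomy. Protocol 5.9 sets the matching aim: "The safety objective is to show that there is no clinically significant difference of product-related adverse events between" the two arms. The SAP's introductory description compares "participants who receive the Axoguard Nerve Cap following neurectomy (Treatment) to those who undergo neurectomy alone (Control"), so both arms undergo neurectomy and only one receives a product.

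**Causality grading.** The heading of Protocol 4.4 covers the control procedure, and its lead-in reads "The Investigator will assess the relationship of each adverse event to the study product and study procedure". The grades in Table 4.4-1 are narrower. Unrelated requires that an event "does not meet the criteria for study device relationship listed" under Possible or Probable, and Definitely Related is "An AE that is clearly and uncontrovertibly due to study device". Protocol 4.5 then tells the investigator to grade each event against the device.

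**Planned summaries.** Protocol 5.9 also says "The safety endpoints will compare the nature and incidence of AEs between treatment groups" and "Separate summaries of treatment-emergent SAEs and AEs related to repair type will be generated". SAP 9.3.2 summarizes AEs by whether they are related to the treatment.

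**Safety set.** Protocol 5.5.2 admits only subjects who received the device and uses that set for every safety analysis. SAP 7.4.4 also admits those who had neurectomy.

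**Recording.** Protocol 1.3 lists six expected local complications that sites need not record unless they worsen. Protocol 4.5 requires all AEs, whatever their cause or clinical importance, from consent until 30 days after the last visit. Protocol 4.1 and the SAP's AE definition tie mandatory recording to placement of the product or device.

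**The concern.** A success criterion that compares two arms has to count the same thing in both. Here the count is tied to something only one arm receives, and the grading table that would supply the count is worded for that arm. The question a reader wants answered is whether adding the cap to neurectomy changes treatment-related harm. A literal reading of 5.10 does not answer it, because part of any difference would come from how events are classified.

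The other two conflicts affect the same comparison. A safety set without controls cannot support the between-arm comparison in 5.9. Two recording rules give sites two answers on which events enter the 3-month AE rate, which is a primary safety endpoint in Protocol 3.5.1 and SAP 9.3.1.

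**Working it through.** The documents state no AE rate, margin or power for safety, so there is no planned figure to reproduce. The check sets the texts side by side and adds simple counts.

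**1. Grades open to an AE clearly caused by neurectomy** (Protocol Table 4.4-1)

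| Grade | Control subject | Cap subject |
|---|---|---|
| Possible (three criteria joined by 'or') | First criterion only: not explained by clinical state or by environmental or toxic factors. The other two refer to the device. | First criterion, or timing after device placement, since both occur in one operation |
| Probable | Closed: the lead-in requires high certainty of a device cause | Listed items could be met, but the same lead-in may block it |
| Definitely Related | Closed: device cause only | Closed: the cause is the neurectomy |

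Grade descriptions that mention the study device: 4 of 4. Grade descriptions that mention the procedure: 0 of 4. Possible criteria not worded for the device: 1 of 3.

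**2. What this does to the 5.10 rates.** The answer depends on a cut-off that neither document gives, so both cases are assumptions.

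- If Possible counts as product-related, control events can qualify and the control rate is not fixed by definition. The two arms still have different routes into the grade.
- If only Probable and Definitely Related count, the literal control count is 0 of 43. As an illustration only (5.10 names no test), Fisher's exact two-sided p for x of 43 against 0 of 43 is 2 × C(43,x)/C(86,x). For x = 5 this gives p = 0.055. For x = 6 (6/43 = 14%) it gives p = 0.026. A difference of that kind would partly reflect the definition.

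**3. Safety set at planned size.** Inputs are 15 pilot and 86 randomized subjects at 1:1 (Protocol 3.1, SAP 7.1), assuming exact balance and treatment as assigned.

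- Per arm: 86/2 = 43.
- Protocol 5.5.2: 15 + 43 = 58 of 15 + 86 = 101 subjects, with 0 of 43 controls. The randomized comparison is 43 versus 0.
- SAP 7.4.4: 58 + 43 = 101 subjects. The randomized comparison is 43 versus 43.

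SAP 8.1 analyses the two phases separately, so 43 versus 0 is the relevant contrast.

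**4. Recording rules.** Four of the six types exempted in Protocol 1.3 (redness, tenderness, edema, numbness) are listed as anticipated adverse events in 4.2. The only exemption in 4.5 is for concurrent or pre-existing conditions, so it does not cover new post-operative signs and does not reconcile the passages. The device-placement trigger in 4.1 and in the SAP definition describes something controls never undergo. The window in 4.5 and the AE review at Visits 2 to 8 in Appendix B apply to all subjects.

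**The case against.** The strongest reply is that the planned analyses already fit both arms. Section 4.4 announces that it covers the procedure; 5.9 compares all AEs between groups and summarizes events by repair type; SAP 9.3.2 uses treatment-relatedness; and SAP 7.4.4 has a workable safety set. On this view only loose wording remains. Much of this stands. It makes the safety-set conflict minor, and it means comparable summaries will exist. It does not settle the first conflict, because 5.10 points to none of those summaries and sites grade events from the Protocol table and from 4.5, both worded for the device.

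A second reply is that replacing product by treatment leaves 5.10 undecidable, since the available text gives no margin, test or decision rule for a clinically significant difference. That is correct, and this point does not claim to cure it. A third is that pooling procedure and device events could dilute device-specific harm such as allergy or protrusion. That also stands and is met in the fix.

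A reader might infer more than the documents support:

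- *That the control rate must be near zero.* This holds only if Possible is excluded, and no cut-off is stated.
- *That 5.10 leaves out most neurectomy-caused harm in cap subjects.* It does not follow, because such events can reach Possible through timing after the device.
- *That minor events will be recorded unequally between arms.* Protocol 1.3 can be read as covering both arms, so this is a possibility only.

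**Conclusion.** The concern holds as three wording conflicts that should be corrected.

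- **Criterion and grading.** The safety part of study success rests on a category that does not fit the control arm, and the grading table allows the same surgical harm to be graded differently by arm. The direction is clear from the text. The size is not, because no document says which grades count as product-related.
- **Safety set.** Followed literally, the Protocol gives 43 versus 0 in the randomized comparison. This is minor, because the SAP already has the definition needed.
- **Recording.** Protocol 1.3 contradicts 4.1 and 4.5 on six event types that bear on a primary safety endpoint. The documents allow no estimate of the effect on AE rates.

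The counts assume 43 per arm, all treated as assigned. The pain endpoint is not affected.

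**What to change.** 1. Restate the 5.9 objective and 5.10 as treatment-related AEs, meaning related to the procedure or the device, to match SAP 9.3.2. State which grades count as related. Word the Table 4.4-1 grades and the grading sentence in 4.5 to cover the procedure in both arms. Keep device-related events as a separate summary.
2. Replace the Protocol 5.5.2 definition with that of SAP 7.4.4.
3. Reconcile Protocol 1.3 with 4.1 and 4.5 into one recording rule applied identically in both arms. Which rule to adopt is for the sponsor to decide. Replace the device-placement trigger in 4.1 and in the SAP's AE definition with arm-neutral wording that fits the 4.5 window.

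**Cost.** A protocol amendment to wording (Protocol 12.1), with a matching edit to the SAP definition. Visits and sample size do not change, and the planned summaries stay, with device-related events shown separately. The documents do not give enrollment status. If subjects have already been treated, AEs graded under the present table would need checking, and events left unrecorded under 1.3 may not be recoverable and should then be disclosed.
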